8.5. ECG Parameters

Electrocardiogram results will be summarized by treatment and visit. Electrocardiogram results will also be listed.

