3.2.5. Electrocardiogram (ECG) Monitoring

Single 12 lead ECGs will be performed as outlined in the Study Flow Chart using sensitive electrodes ensuring the subject's skin is not harmed from the procedure (e.g. SofTouch™ Electrodes). The ECGs will be performed on subjects in supine position. The following ECG data will be collected:

- Heart rate
- PR interval
- QRS duration
- QT interval
- RR interval
- Overall Interpretation

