8.3. Safety Laboratory Parameters

Clinical laboratory results will be summarized with descriptive statistics by treatment and visit. Change from baseline will also be summarized. Laboratory values will also be listed by visit, within patient.

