8.4. Vital Signs

Vital signs and the change from baseline will be summarized descriptively by treatment and visit. The count and percentage of subjects with abnormal values will be summarized by treatment and visit. Abnormal blood pressure measurements for subjects age 17 and younger will be defined as either systolic or diastolic measurements above the 95th percentile, according to height, sex, and age. Abnormal blood pressure measurements for subjects age 18 and older will consist of either a systolic blood pressure >140mm Hg or a diastolic blood pressure >90mm Hg. Abnormal weight measurements for subjects age 18 and older will be defined as measurements > 300 pounds (>118 kilograms). Abnormal BMI measurements for subjects age 17 and younger will be defined as measurements above the 95th percentile, according to sex and age. Abnormal values will be defined as clinically relevant (CR) or not clinically relevant (NCR) on the eCRFs. Vital sign data will also be listed by visit, within patient.

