8.6. Physical Examinations

Physical examinations and the change from baseline will be summarized by treatment and visit. Physical examination results will also be listed by visit, within patient.

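### The SAP summarizes uncorrected QT by arm and visit, with no rate-corrected QT and no change from baseline, although the data for both are collected

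*SAP*

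**What the plan says.** SAP 3.2.5 specifies the recording ("Single 12 lead ECGs will be performed as outlined in the Study Flow Chart using sensitive electrodes") and then, under "The following ECG data will be collected", lists heart rate, PR, QRS, QT, RR and "Overall Interpretation". Neither document names a corrected QT, a correction formula or an outlier category.

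SAP 8.5 gives the whole ECG analysis in two sentences: "Electrocardiogram results will be summarized by treatment and visit" and "Electrocardiogram results will also be listed". The neighbouring sections go further:

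- Laboratory values, SAP 8.3: "Change from baseline will also be summarized".
- Vital signs, SAP 8.4: "Vital signs and the change from baseline will be summarized descriptively by treatment and visit". Counts of abnormal values are added, with age-specific limits for blood pressure.
- Physical examinations, SAP 8.6: "Physical examinations and the change from baseline will be summarized by treatment and visit".

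By the visit descriptions, ECGs are taken at Visit 2 before randomization (Protocol 8.2.2), at Visit 6, the end of treatment (8.2.6), and at Visit 8, eight weeks later (8.2.8). SAP 6.3 already defines baseline for all analysis variables. Protocol 11.2.4 names ECGs as a safety measure without describing an analysis. Subjects are 4 years or older with no upper limit stated (Protocol 7.3), and randomization is stratified by age only at 8 years.

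**The concern.** QT shortens as heart rate rises, so a raw QT value cannot be read without the rate at which it was recorded. Resting rates can be expected to differ between young children and adults, and from visit to visit within a subject. A table of raw QT by arm and visit carries both sources of variation into the comparison. If the arms differ in heart rate, by chance or through the drug, the raw contrast mixes that difference with any change in repolarization.

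Leaving out change from baseline adds to this, because stable between-subject differences stay in the comparison and individual shifts are not tabulated. At stake is how readable the trial's repolarization data are. No efficacy result depends on it.

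**Working it through.** The documents give no QT figure to reproduce. The check is whether realistic rate changes move raw QT by an amount that matters.

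**Inputs.** From the documents: QT, RR and heart rate are recorded (SAP 3.2.5); about 80 subjects are randomized 1:1 (SAP 2.2), so about 40 per arm. Assumed, because the documents give no values: QTcF of 400 ms, heart rates of 70 to 100 bpm, a true effect of 10 ms, and all standard deviations.

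**Formula.** Fridericia: QTcF = QT / RR^(1/3), with RR = 60/HR in seconds. Hence QT = QTcF × (60/HR)^(1/3).

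**Rate change alone, QTcF fixed at 400 ms.**
- 70 to 65 bpm: 400 × (60/65)^(1/3) − 400 × (60/70)^(1/3) = 389.5 − 380.0 = +9.5 ms.
- 100 to 95 bpm: 400 × (60/95)^(1/3) − 400 × (60/100)^(1/3) = 343.2 − 337.4 = +5.8 ms.

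With Bazett (exponent 1/2) the same two falls give +14.0 and +8.0 ms.

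**A true rise of 10 ms in QTcF (400 to 410).** Raw QT is unchanged when the rate rises by the factor (410/400)^3 = 1.0769.

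| Starting rate (bpm) | Raw QT at QTcF 400 (ms) | 5 bpm fall, QTcF unchanged (ms) | 5 bpm rise, QTcF +10 (ms) | Rate rise that cancels +10 ms (bpm) |
|---|---|---|---|---|
| 70 | 380.0 | +9.5 | +0.6 | 5.4 |
| 80 | 363.4 | +7.9 | +1.6 | 6.2 |
| 90 | 349.4 | +6.7 | +2.3 | 6.9 |
| 100 | 337.4 | +5.8 | +2.9 | 7.7 |

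After correction, each case returns the true 0 or +10 ms. The second column also shows the between-subject effect: at one and the same QTcF, raw QT differs by about 43 ms between 70 and 100 bpm.

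**How large a chance rate imbalance could be.** With an assumed SD of heart-rate change of 10 to 15 bpm, the standard error of the arm difference is SD × √(2/40) = 2.2 to 3.4 bpm. A 5 bpm imbalance is then about 1.5 to 2.2 standard errors, and a 10 bpm imbalance about 3.0 to 4.5.

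**What 40 per arm can resolve.** The 95% half-width for a difference in means is 1.96 × SD × √(2/40). For SDs of 15, 20, 30 and 40 ms it is 6.6, 8.8, 13.1 and 17.5 ms. Any reduction in SD from using QTc and change from baseline narrows the comparison, but an effect of a few milliseconds stays out of reach throughout this range.

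**The case against.** A reader might infer that the planned ECGs cannot show a QT effect at all, or that arm means of raw QT mostly reflect age mix and heart rate. The documents do not support either reading.

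- **Randomization.** Allocation is 1:1 and stratified at age 8, so age and heart rate balance between arms in expectation. The age range mainly adds variance. A chance imbalance is part of ordinary sampling error, and systematic distortion would need a drug effect on heart rate, which nothing in the documents suggests.
- **Rate is displayed.** ECG heart rate and RR fall under the same by-arm summary as QT, and pulse rate gets change from baseline under SAP 8.4. A rate difference large enough to hide a sizeable QT effect would be visible.
- **Arm mean change is nearly available.** With complete data it is the difference between the visit means. What is lost is the SD of change and the counts of individual shifts.
- **Individuals have cover.** A physician reviews every tracing (Protocol 9.3.2), clinically significant findings are reported as adverse events (Protocol 10.1), and all results are listed.
- **The documents raise no QT signal.** Neither list of events of special interest names a cardiac event. Protocol 3 reports serum rhein below 1% of the level after a single oral dose, although from only two patients using the cream on 3% BSA, against up to 30% BSA here.
- **The design limits sensitivity.** Each ECG is a single tracing, and only Visit 6 falls at the end of treatment. Correction cannot change that.

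All of this stands and lowers the weight of the point. It does not remove the omission. Review of single tracings will not reveal a modest shift in an arm mean, and a reader given separate tables of raw QT and heart rate has to combine them by eye. SAP 8 leaves room for other safety summaries as appropriate, but choosing a formula and cut-offs after unblinding is weaker than stating them beforehand.

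**Conclusion.** The point holds as a minor gap in the safety analysis. The plan summarizes uncorrected QT without change from baseline, although RR and a Visit 2 ECG are collected and three neighbouring safety domains get change from baseline. Under an assumed QTcF of 400 ms and rates of 70 to 100 bpm, a 5 bpm fall lengthens raw QT by about 6 to 10 ms, and a rise of 5.4 to 7.7 bpm cancels a true 10 ms effect. The summary is therefore noisier than it needs to be, and a between-arm rate difference could partly mask or mimic a QT shift.

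These figures show the mechanism. They do not predict that such a rate difference will occur. Nor would correction let the trial exclude a small QT effect: with single ECGs and about 40 per arm, the half-width is 6.6 to 17.5 ms for assumed SDs of 15 to 40 ms. The primary and key secondary conclusions are unaffected.

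**What to change.** Amend SAP 3.2.5 and 8.5 before database lock, up to which SAP 1 allows revisions:

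1. Derive QTc from recorded QT and RR with one prespecified formula, for example Fridericia.
2. Summarize QTc and the other intervals as value and change from the Visit 2 baseline, by arm, at Visits 6 and 8.
3. Add counts of subjects above prespecified categories of QTc value and QTc change. The documents give no basis for particular limits, so the sponsor should choose the cut-offs and justify them for children and for adults.

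Both value and change are needed with the correction: change from baseline removes stable differences between subjects, and QTc removes rate shifts within a subject.

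The cost is one derived variable and one or two extra tables, with no new ECGs, visits or data collection.

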8.6. Physical Examinations

Physical examinations and the change from baseline will be summarized by treatment and visit. Physical examination results will also be listed by visit, within patient.

8.7. Pharmacokinetic Analysis

Blood draws for PK sampling and modeling will be obtained at the timepoints listed in the Study Flow Chart (see Table 1). Quantification of diacerein and its active metabolite, rhein in patient plasma will be performed using a validated bioanalytical assay. Data permitting, population PK and pharmacokinetic/pharmacodynamic (PK/PD) analyses will be performed. A separate Pharmacokinetic Analysis Plan will be prepared describing the details regarding the PK analysis, including the data handling and methods for the analysis.

9. DATA MONITORING COMMITTEE

An independent data monitoring committee (DMC) will monitor the safety of subjects over the course of the study. An interim analysis will also be conducted by the DMC. Details related to the DMC responsibilities, authorities, and procedures will be documented in the DMC charter. After each meeting, the DMC will advise whether any changes to the conduct of the study are necessary.

10. INTERIM ANALYSIS

An interim analysis of the two confirmatory endpoints (primary endpoint, key secondary endpoint) for efficacy, futility, and sample size re-estimation will be conducted by an independent data monitoring committee (DMC) when 40 subjects (50% of the planned total sample size) have completed Visit 6 (Week 8). The Sponsor and the study investigators will remain blinded. Following the interim analysis, the DMC will make one of the following four recommendations to the Sponsor:

- Terminate the study for futility.
- Continue the study as planned.
- Increase the sample size to $n=XXX$ subjects, where the maximum value of XXX is equal to 200.
- Terminate the study on the basis of having demonstrated overwhelming evidence of efficacy.

Based on the Lan-DeMets method for group sequential trials using O'Brien-Fleming boundaries ([Reboussin, 2000](#)), the levels of significance for the interim and final analyses corresponding to a single interim analysis at the 50% information fraction are $\alpha=0.00305$ and $\alpha=0.049$, respectively.

If the two-sided p-values at the interim analysis for both the primary efficacy endpoint and the key secondary endpoint are less than 0.00305, then the DMC may recommend to the sponsor that the trial be terminated early for efficacy.

If the DMC does not recommend early termination for efficacy, then the conditional power ([Jennison, 2000](#)) for the final analysis of the primary endpoint will be computed under the assumption that the treatment difference and variability observed at the interim analysis represent the true values of the unknown parameters. If the estimated conditional power for the final analysis of the primary endpoint is less than 10%, then the DMC may recommend to the sponsor that the trial be terminated early for futility.

If the DMC does not recommend early termination (for efficacy or futility), then for each of the two endpoints (primary endpoint, key secondary endpoint), the sample size required to achieve 80% power at the final analysis will be re-estimated based on the treatment difference and variability observed at the interim analysis. The DMC may then recommend that the sample size be increased to the larger of the two sample size estimates in order to maintain 80% power.

Due to the sample size re-estimation component of the interim analysis, the final analysis will be conducted using the approach of Cui, Hung, and Wang. ([Cui, 1999](#))

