11.4. Sample Size Calculation

Suppose the percentage of subjects with $\geq 40\%$ reduction in BSA of EBS lesions at Week 16 are 60% and 30%, in Diacerein 1% Ointment or Control Ointment, respectively. Based on a two-

sided, two-sample parallel design for large sample test of proportions with a power of 80% and significance level of 0.05⁷, the sample size needed for a fixed sample size design without interim analysis and sample reconsideration is:

$$n_1 = n_2 = \frac{(z_{\alpha/2} + z_{\beta})^2 (p_1(1-p_1) + p_2(1-p_2))}{(p_2 - p_1)^2} = \frac{(1.96 + 0.84)^2 (0.6 \times (1-0.6) + 0.3 \times (1-0.3))}{(0.6 - 0.3)^2} \approx 39.$$

One interim analysis is planned and sample size will be reconsidered then. We employ O'Brien and Fleming's method⁷, and the sample size is inflated to:

$$n'_1 = n'_2 = n_1 R_B(2, 0.05, 0.2) = 39 \times 1.008 \approx 40,$$

in which $R_B(2, 0.05, 0.2) = 1.008$ is the O'Brien and Fleming's method constant for two-sided test with $\alpha = 0.05$ and $power = 1 - 0.2 = 0.8$.

Thus, at the interim analysis, the sample size per treatment group is $40/2 = 20$. The conditional power will be calculated at the interim analysis, based on which the sample size will be recalculated.

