11. SAMPLE SIZE AND POWER CONSIDERATIONS

The original sample size calculation was based on the endpoint of the proportion of subjects with $\geq 40\%$ reduction in BSA of EBS lesions at Week 16. The assumed true rates were 60% and 30% in the Diacerein 1% Ointment and Control Ointment groups, respectively. Based on a two-sided, two-sample comparison of proportions at the $\alpha=0.049$ level of significance, a total sample size of 80 subjects provides 77% power. No data are available on which to base a sample size calculation for the primary endpoint, now defined at Week 8 and now based on the proportion of subjects with $\geq 60\%$ reduction in BSA.

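### Does SAP 10 need a written rule for a re-estimated sample size above 200?

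*SAP*

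**What the plan says.** SAP 10 places one interim analysis after 40 of 80 subjects complete Week 8. Early stopping for efficacy needs both endpoints to cross 0.00305. Futility is judged on the primary endpoint only: "If the estimated conditional power for the final analysis of the primary endpoint is less than 10%, then the DMC may recommend" stopping. Otherwise BSA and IGA each get their own calculation, in which "the sample size required to achieve 80% power at the final analysis will be re-estimated based on the treatment difference and variability observed". From these two results, the DMC may recommend that the total be "increased to the larger of the two sample size estimates in order to maintain 80% power".

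Among the four possible recommendations are "Continue the study as planned" and an increase to n=XXX, "where the maximum value of XXX is equal to 200". The final analysis uses the Cui-Hung-Wang approach at a two-sided level of 0.049.

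Three other statements bear on this. Protocol 11.4 describes the recalculation as "The conditional power will be calculated at the interim analysis, based on which the sample size will be recalculated". SAP 11 says of the endpoint as now defined: "No data are available on which to base a sample size calculation for the primary endpoint". SAP 9 says: "Details related to the DMC responsibilities, authorities, and procedures will be documented in the DMC charter". The protocol (Synopsis, 11.3 and 12.4) also leaves interim details to the charter, which is not among the documents.

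**The concern.** Read literally, SAP 10 leaves three things unsaid.

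1. If the larger estimate exceeds 200, the trial could go to 200, which does not reach 80% power at the observed rates, or stay at 80, which is also on the list of recommendations.
2. If the interim IGA difference is zero or negative, no IGA sample size exists. Futility looks only at BSA, so such a trial can continue.
3. No formula is named, and the protocol speaks of conditional power where the SAP speaks of power at the final analysis.

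Since there are no data to size the current primary endpoint, re-estimation is its main protection against low power. If 80 and 200 were equally plausible outcomes, the choice would be made on unblinded data and would shift power for both confirmatory endpoints.

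**Working it through.** **Inputs.** From SAP 10 and 11: 20 per arm at the interim, planned total 80, maximum 200, final two-sided level 0.049 (critical value 1.969), target power 80% (0.842), futility below 10% conditional power, rates 60% and 30% for the earlier BSA endpoint. Cui-Hung-Wang weights are √0.5 per stage. IGA rates, other BSA rates and the BSA-IGA correlation are assumptions.

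**The plan's own figure.** With 40 per arm, 60% versus 30%, level 0.049 and pooled variance, power is 77.7%. SAP 11 states 77%. It reproduces.

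**How far the unstated zone extends for BSA.** With interim statistic z and n₂ further subjects per arm, conditional power under the observed trend is

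Φ(z√(n₂/20) + z − 1.969/√0.5) = Φ(z√(n₂/20) + z − 2.784).

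- At the planned size n₂ = 20, so this is Φ(2z − 2.784). It equals 10% at z = 0.751.
- The required total is about 40 × (2.810/z)². It exceeds 200 when z < 2.810/√5 = 1.257, where conditional power at 80 is 39%.
- So trials with conditional power from 10% to about 39% pass futility yet need more than 200.

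**Worked case, BSA 9/20 versus 6/20.** Per arm, unpooled: 2.810² × (0.45×0.55 + 0.30×0.70)/0.15² = 160.6, so 322 in total (328 pooled). With pooled z = 0.980:

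- at 80: Φ(0.980 + 0.980 − 2.784) = 20%
- at 200 (n₂ = 80): Φ(1.960 + 0.980 − 2.784) = 56%

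**Where continuing as planned naturally applies.** BSA 12/20 versus 6/20, the planned rates, gives 2.810² × (0.24 + 0.21)/0.30² = 39.5 per arm, so 80 in total (86 pooled). That option therefore has an obvious use at the low end of the estimates.

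**BSA estimate alone.** Exact enumeration of both stages, pooled statistics, no efficacy stop, power over all trials including futility stops:

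| True rates | Chance of passing futility with estimate above 200 | Power if 200 | Power if 80 | Difference |
|---|---|---|---|---|
| 60/30 | 8% | 84.0% | 80.8% | 3.2 points |
| 50/30 (assumed) | 12% | 55.7% | 49.9% | 5.8 points |
| 40/20 (assumed) | 15% | 60.4% | 53.0% | 7.4 points |

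**Larger of the two estimates.** Simulation with BSA at 60/30, latent correlations 0.3 to 0.8 and three sample size formulas; a non-positive IGA difference adds no estimate. BSA power is 84–86% if above-200 estimates give 200, and 79–81% if they give 80. IGA power after BSA is 51–54% versus 36–40% (IGA 30/15), 64–68% versus 48–53% (40/20), and 81–83% versus 71–75% (50/20).

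**Type I error.** In the exact BSA calculation the one-sided error at equal rates (30/30 and 20/20) is 2.2–2.3% under either reading.

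**The two smaller points.** Once 200 is taken as the cap, using only the BSA estimate for an undefined IGA, instead of 200, changes IGA power by about 1 to 2 points and BSA power by under 1. Conditional rather than unconditional power changes individual estimates (BSA 11/20 versus 6/20: 98–106 against 116–122), but overall BSA power by at most about 1.5 points.

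**The case for a change.** The strongest case for a change is that the above-200 zone is not rare, that the SAP's change table (SAP 12, Table 2) presents Section 10 as the place where the DMC's recommendations and the 200 limit were made more specific, and that one sentence would settle it. Discretion to decline an increase also differs from having no stated default.

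Part of this stands. The text is incomplete, and the phrase about maintaining 80% power cannot be true at the observed rates once the estimate passes 200. It can only mean a target.

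The rest carries less weight. The large power differences arise only if a DMC reads a stated maximum of 200 as a reason to stay at 80. A written cap would also leave the DMC's recommendation permissive, so it would not secure the whole difference. Choosing a size on unblinded data is inherent in this design: SAP 10 gives the task to an independent DMC and keeps the sponsor and investigators blinded.

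Nor is every added rule an improvement. Dropping IGA whenever its difference is not positive creates a jump. IGA 4/20 versus 3/20 requires 2.810² × (0.16 + 0.1275)/0.05² = 908.2 per arm, about 1,800 in total, and so leads to 200. IGA 4/20 versus 4/20 would be ignored and could leave a trial of about 80. The worse IGA result would give the smaller trial.

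**Conclusion.** The concern describes missing detail, and the plan's inference does not depend on it. An analyst or DMC statistician would take the maximum as a cap and continue at 80 when the estimate is about 80 or less, with procedural detail looked for in the charter. On that reading the design works and the type I error is controlled.

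Even on the unlikely reading, the BSA estimate alone at 60/30 costs about 3 points of BSA power, and power stays at about 80%. This uses rates set for the superseded endpoint. The 6 to 7 point BSA differences at lower rates, and the IGA differences of 8 to 17 points, rest on rates and correlations that the documents do not supply. The undefined-IGA and formula points are worth about 1 to 2 points each. What the charter says is unknown here, but the conclusion does not require it to cover these cases. No change to the plan follows.

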11. SAMPLE SIZE AND POWER CONSIDERATIONS

The original sample size calculation was based on the endpoint of the proportion of subjects with $\geq 40\%$ reduction in BSA of EBS lesions at Week 16. The assumed true rates were 60% and 30% in the Diacerein 1% Ointment and Control Ointment groups, respectively. Based on a two-sided, two-sample comparison of proportions at the $\alpha=0.049$ level of significance, a total sample size of 80 subjects provides 77% power. No data are available on which to base a sample size calculation for the primary endpoint, now defined at Week 8 and now based on the proportion of subjects with $\geq 60\%$ reduction in BSA.

